# 2.3.3 Exploratory Objective Estimands

Exploratory objectives have efficacy, safety, and outcomes research endpoints. The estimands corresponding to the exploratory objectives are shown in Table 3.

**Table 3: Exploratory Objective Estimands** 

.	
Objective	Return to Normal Function at 24 hours post-dose – Efficacy
	Percentage of subjects with normal function at 24 hours post-dose and no intervening
Endpoint	rescue medication taken at or before 24 hours post-dose; evaluated for subjects with
	functional disability at on-study migraine attack onset
Intercurrent Events	Composite strategy: Intercurrent event captured in endpoint definition
Pop. Summary	Percentage of subjects by treatment group
Objective	Preference of Medication (PoM) – Outcomes Research
Endpoint	Percentage of subjects who prefer study medication to previous migraine medications;
Enupoint	evaluated for those with PoM data
Intercurrent Events	Treatment policy strategy: No accounting for intercurrent events
Pop. Summary	Percentage of subjects by treatment group
Objectives	Pain Freedom at all time points post-dose – Efficacy
Population	mITT
-	Percentage of subjects with no pain at each time point post-dose and no intervening
Endpoint	rescue medication taken at or before the time point
Intercurrent Events	Composite strategy: Intercurrent event captured in endpoint definition
Pop. Summary	Percentage of subjects by treatment group
Objectives	Pain Relief at all time points post-dose – Efficacy
ū	Percentage of subjects with mild or no pain at each time point post-dose and no
Endpoint	intervening rescue medication taken at or before the time point
Intercurrent Events	Composite strategy: Intercurrent event captured in endpoint definition
Pop. Summary	Percentage of subjects by treatment group
Objectives	MBS Freedom at all time points post-dose – Efficacy
Objectives	Percentage of subjects with (1) MBS absent at each time point post-dose, (2) MBS
Endpoint	reported at on-study migraine attack onset before study drug, and (3) no intervening
Znapomi	rescue medication taken at or before the time point
Intercurrent Events	Composite strategy: Intercurrent event captured in endpoint definition
Pop. Summary	Percentage of subjects by treatment group
Objectives	Return to Normal Function at all time points post-dose – Efficacy
Objectives	Percentage of subjects with normal function at each time point post-dose and no
Endpoint	intervening rescue medication taken at or before the time point; evaluated for subjects
Znapome	with functional disability at on-study migraine attack onset
Intercurrent Events	Composite strategy: Intercurrent event captured in endpoint definition
Pop. Summary	Percentage of subjects by treatment group
Objectives	Migraine Quality of Life Questionnaire (MQoL) – Outcomes Research
Endpoint	Change from baseline in the total score at end of treatment visit
Intercurrent Events	Treatment policy strategy: No accounting for intercurrent events
Pop. Summary	Mean change from baseline in total score by treatment group
Objective	Safety and Tolerability
Objective	Frequency of adverse events (AEs) of at least moderate severity, serious adverse
Endpoint	events (SAEs), and clinically relevant laboratory test abnormalities
Intonouguant Events	
Intercurrent Events	Treatment policy strategy: No accounting for intercurrent events
Pop. Summary	Number and percentage of subjects with safety events and findings
Objective	Sheehan Suicidality Tracking Scale – Safety
Endpoints	Change from baseline in the total score at end of treatment visit
Intercurrent Events	Treatment policy strategy: No accounting for intercurrent events
Pop. Summary	Percentage of subjects in each change from baseline category (< -1, -1, no change, 1, >
- vp. vammar j	1) by treatment group

#### 3 POPULATION SAMPLES FOR ANALYSES

The following population samples for analyses ("analysis sets") will be evaluated and used for presentation and analysis of the data:

- Enrolled subjects: Subjects who sign an informed consent form and are assigned a subject identification number, i.e., non-missing informed consent date.
- Randomized subjects: Enrolled subjects who receive a randomization treatment assignment from the interactive web response system (IWRS), i.e., non-missing IWRS randomization date.
- Treated subjects: Enrolled subjects who take study therapy (BHV-3500 or placebo), i.e., non-missing study drug start date/time.
- Modified Intent-to-Treat (mITT) subjects: Treated subjects who are randomized only once, have moderate to severe pain at on-study migraine attack onset, and have non-missing, post-baseline efficacy data (i.e., non-missing pain level, phonophobia status, photophobia status, nausea status, or functional disability level with finding date/time from the eDiary Post-Dose Migraine Report at any time point after the study drug start/time).

See Section 7.3 for derived dates.

#### 4 SCHEDULE OF ANALYSES

All analyses described in this SAP will be performed after the last subject completes the end of treatment visit or discontinues from the study, and the database has been locked.

#### 5 SAMPLE SIZE AND POWER

If 95% of the 400 subjects randomized to each treatment group treat a migraine on study, then there will be roughly 380 mITT subjects in each treatment group.

If the true response rates for pain freedom at 2 hours are 22% and 12% in the BHV-3500 and placebo groups, then a chi-square test at alpha=0.0167 will have 90% power. Similarly, if the true response rates for MBS freedom at 2 hours are 45% and 32% in the BHV-3500 and placebo groups, then a chi-square test at alpha=0.0167 will have 90% power. Under the assumption that the endpoints are independent, the power for both endpoints jointly is roughly 80%.

#### **6 STATISTICAL METHODS**

Tables will present results by treatment group (i.e., BHV-3500 5 mg, BHV-3500 10 mg, BHV-3500 20 mg, Placebo) and All BHV-3500 with the following exceptions:

- Results for enrolled subjects will be presented only by overall, without treatment group and All BHV-3500.
- Results for study population parameters (see Section 6.2) and pre-treatment safety will include overall, unless specified otherwise.
- Efficacy results for mITT subjects will be presented only by treatment group, without All BHV-3500 and overall.

The "All BHV-3500" treatment group will consist of subjects pooled across the three BHV-3500 treatment groups. Because this group is intended mainly to support safety, it will be included only in tables for the population samples of randomized subjects and treated subjects.

The population sample of treated subjects will be assessed by as-treated treatment group, i.e., by the treatment actually received, unless specified otherwise. Otherwise, all other population samples (i.e., randomized, mITT) will be assessed by as-randomized treatment group.

All statistical analyses will be performed using SAS statistical software (Version 9.4 or higher).

Medical history and AEs will be coded using Medical Dictionary for Regulatory Activities (MedDRA). Non-study medications will be coded using World Health Organization Drug Dictionary (WHO-DD). Refer to the latest version of Biohaven Dataset Guidelines for dictionary versions.

#### 6.1 General Methods

#### 6.1.1 Missing Data

For all binary efficacy endpoints, principal analyses will impute missing data as failure using methods described in Section 6.3.1 Sensitivity analysis of the co-primary endpoints will exclude subjects with missing data or impute missing data using different methods (see Section 6.3.3.1 and Section 6.3.3.2). Sensitivity analysis of exploratory efficacy endpoints will exclude subjects with missing data (see Section 6.3.5.2). Otherwise, all analyses will be based on observed data without using imputation.

# 6.1.2 Type I Error Control

Type I error will be controlled by a hierarchical gate-keeping procedure. First, the family of two co-primary endpoints will be tested. In particular, each BHV-3500 treatment group will be tested for superiority against placebo at a Bonferroni corrected alpha=0.0167 level for both co-primary endpoints. If both co-primary endpoint tests are determined to be significant for a BHV-3500 treatment group versus placebo, then the secondary endpoints will be tested for that BHV-3500 treatment group versus placebo using a hierarchical gate-keeping procedure, with each test in the hierarchy conducted at alpha=0.0167.

The secondary endpoints will be tested in the order shown in Section 1.2.2.

If a test in the hierarchy is not significant, then any further tests on endpoints in the sequence will have p-values presented only for descriptive purposes, and no conclusions will be drawn from those results.

For exploratory endpoints, no attempt will be made to adjust for multiplicity. Any exploratory endpoints for which p-values are produced will be evaluated at an unadjusted two-sided alpha level of 0.05 and presented only for descriptive purposes.

# 6.1.3 Subgroups

For mITT subjects, the following efficacy subgroups are of interest:

- Age:  $< 40, \ge 40 \text{ years}$
- Sex: female, male
- Race: White, Black or African American, Other including Asian, Asian
- Ethnicity: Hispanic or Latino, Not Hispanic or Latino
- Baseline body mass index (BMI; kg/m^2):  $< 25, \ge 25$  to  $< 30, \ge 30$
- Aura at on-study migraine attack onset: yes, no
- Historical number of moderate or severe migraine attacks per month: < median, ≥ median, where the median is calculated overall across treatment groups combined for mITT subjects and rounded to an integer.
- Triptan non-responder: yes, no (see Section 7.2).

Subgroup analyses will be performed for the co-primary efficacy endpoints only. Efficacy subgroup tables will present results by subgroup level for subjects with non-missing subgroup level data, unless specified otherwise.

Subgroup levels may be redefined or combined based on the availability of data.

# 6.2 Study Population

# 6.2.1 Population Samples for Analyses and Randomization

The number of subjects in each population sample for analysis described in Section 3 will be presented by as-randomized or as-treated treatment group, not randomized, and overall.

Inclusion and exclusion from the mITT population will be summarized by treatment group and overall as the number and percentage of randomized subjects in the following categories:

- Included in mITT population
- Excluded from mITT population
  - Treated
    - Pain level of mild, none, or not reported at on-study migraine attack onset
    - Randomized more than once
    - No post-baseline efficacy data (i.e., missing all of the following parameters from the eDiary Post-Dose Migraine Report after the study drug start date/time: pain level, nausea status, phonophobia status, photophobia status, and functional disability level)
  - Not treated.

A by-subject listing of population samples for analyses will be provided for enrolled subjects. The listing will flag subjects in population samples, and include as-treated treatment group only if different from as-randomized treatment group.

A by-subject listing of subjects excluded from the efficacy analysis will be provided for randomized subjects not in the mITT population sample, including the reason for exclusion (e.g., not treated). Treated subjects may have more than one exclusion reason.

A by-subject administrative listing of randomization scheme and codes will be provided for all randomization numbers and block numbers, even those not assigned to a subject. This listing will be sorted by randomization number and block number, and will contain the randomization number, site-subject ID, treatment group, randomization stratum, and randomization date.

# 6.2.2 Subject Disposition

Subject disposition will be based on the Study Exit Status case report form (CRF), unless noted otherwise.

Subject disposition from enrollment to randomization will be summarized for enrolled subjects by overall as the number and percentage of subjects in the following categories:

- Randomized
- Not randomized
  - Reasons for not completing the study, including not reported (e.g., adverse event, death).
     For subjects whose reason is screen failure due to inclusion/exclusion criteria, the reasons for screen failure will be also be included from the Inclusion/Exclusion Findings Summary CRF.

Subject disposition from randomization to treatment will be summarized for randomized subjects by as-randomized treatment group, All BHV-3500, and overall as the number and percentage of subjects in the following categories:

- Treated
- Not treated
  - o Reasons for not completing the study, including not reported.

Subject disposition during the treatment phase will be summarized for treated subjects by astreated treatment group, All BHV-3500, and overall as the number and percentage of subjects in the following categories:

- Completed study
- Did not complete study
  - o Reasons for not completing the study, including not reported.

Subject disposition during the treatment phase will be summarized analogously for mITT subjects by as-randomized treatment group and overall to support efficacy.

The following by-subject listings will be provided for enrolled subjects: (1) subject disposition, including the informed consent date, randomization date, study drug start date/time, last contact date, and reason for not completing the study, if applicable; (2) eligibility with inclusion and exclusion criteria for all subjects, not just those who have non-missing criteria.

See Section 7.3 for derived dates.

#### 6.2.3 Protocol Deviations

A significant protocol deviation is any deviation that could impact subject safety or the integrity of the trial, and are defined as follows:

- Informed Consent
- Inclusion Criteria (Specify criteria #)
- Exclusion Criteria (Specify criteria #)
- Concomitant Medication
- SAE Reporting
- Regulatory
- Drug Storage/ Preparation
- Drug Administration
- Visit Schedule
- ePRO Diary Noncompliance
- Noncompliance (i.e. trends, missed assessments)

The number and percentage of treated subjects with significant protocol deviations will be summarized by deviation type and by as-randomized treatment group, All BHV-3500, and overall. Deviation types will be presented in descending order of overall frequency.

A by-subject listing of significant protocol deviations will be provided for enrolled subjects.

#### 6.2.4 Pre-Treatment Characteristics

Demographics and baseline characteristics, medical history, migraine history, cardiac and other risk factors, prior triptan response, and current triptan response, and migraine characteristics at on-study migraine attack onset will be summarized by as-randomized treatment group and overall for mITT subjects to support efficacy. These endpoints will also be summarized for treated subjects by as-treated treatment group, All BHV-3500, and overall to support safety.

In addition, demographics and baseline characteristics and migraine history will be summarized for (1) subjects enrolled but not randomized by overall only, and (2) subjects randomized but not in the mITT population by as-randomized treatment group, All BHV-3500, and overall.

Tables will display a "not reported" category for missing categorical variables, if applicable.

Prophylactic migraine medication use at randomization (yes, no) will be summarized by asrandomized treatment group, All BHV-3500, and overall for randomized subjects.

Baseline is defined according to population as follows:

- Enrolled subjects not randomized: Last non-missing value
- Randomized subjects not treated: Last non-missing value at or before the IWRS randomization date/time
- mITT subjects and treated subjects: Last non-missing value at or before the study drug start date/time (i.e., in the pre-treatment analysis period; see Sections 7.4 and 7.5).

The following by-subject listings of pre-treatment characteristics will be provided:

- Demographics, displaying informed consent date, birth date, age, sex, race, and ethnicity. All reported races will be displayed comma-concatenated alphabetically for subjects who reported multiple races (e.g., "Asian, White").
- Baseline characteristics (see Section 6.2.4.1).
- Medical history, displaying start date, stop date or ongoing, system organ class (SOC), preferred term (PT), and verbatim term.
- Migraine history split into general migraine history, migraine without aura symptom history, and migraine with aura symptom history.
- Cardiac and other risk factors for subjects with any risk factor present. Only records with "yes" responses to questions about having risk factors will be displayed.
- Prior triptan response, displaying triptan name, route, discontinuation reason, and symptom frequency.
- Current triptan response, displaying triptan name, route, and frequency of symptom relief.

#### 6.2.4.1 Demographics and Baseline Characteristics

Demographics will include the following:

- Age (years) at informed consent calculated as: (informed consent date birth date + 1) / 365.25 truncated to an integer, also categorized as  $< 40, \ge 40, < 65, \ge 65$
- Sex (male, female)
- Childbearing potential, if female (yes, no)
- Race (White, Black or African American, other including Asian [i.e., American Indian or Alaska Native, Asian, Native Hawaiian or Other Pacific Islander, multiple]). Subjects with more than one race are counted only in the "multiple" category.
- Ethnicity (Hispanic or Latino, not Hispanic or Latino).

Baseline characteristics will include the following:

- Height (cm)
- Weight (kg)
- BMI (kg/m^2), also categorized as  $< 25, \ge 25$  to  $< 30, \ge 30$
- Prophylactic migraine medication use at randomization (yes, no), i.e., IWRS randomization strata.

#### 6.2.4.2 Medical History

Medical history will be summarized by SOC and PT, and displayed in descending order of overall frequency within SOC and PT.

## 6.2.4.3 Migraine History

Migraine history will include the following:

- Age (years) at migraine onset
- Time since last migraine (days) calculated as: (informed consent date imputed last migraine date) for subjects with imputed last migraine date up to 1 year before informed consent date. Last migraine date will be imputed for partial dates using the same methodology as AE start dates, but using the informed consent date as the surrogate date (see Section 7.6.1.1 for AE start date imputation). If the last migraine date is missing, then it will be imputed with the informed consent date.
- Number of moderate to severe migraines per month, also categorized as < median and ≥ median (see Section 6.1.3)
- Average duration of untreated migraine attacks (hours)
- Primary migraine type (migraine without aura, migraine with aura)
- Most bothersome symptom (i.e., nausea, phonophobia, or photophobia)
- Migraine symptoms (i.e., headache attacks lasting 4-72 hours, unilateral location, pulsating quality, moderate or severe pain level, aggravation by or causing avoidance of routine physical activity, during headache: nausea and/or vomiting, during headache: photophobia and phonophobia)
- History of migraine without aura (yes, no)
- History of migraine with aura (yes, no). For subjects with a "yes" response to this question:
  - o Aura symptoms (i.e., visual, sensory, speech and/or language, motor, brainstem, retinal)
  - Aura characteristics (i.e., at least one aura symptom spreads gradually over ≥ 5 min, and/or two or more symptoms occur in succession; each individual aura symptom lasts 5-60 min; at least one aura symptom is unilateral; the aura is accompanied, or followed within 60 min, by headache)

o Migraine with aura type (i.e., migraine with typical aura, typical aura with headache, and typical aura without headache).

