## 7.6 Domain-Specific Derivations

### 7.6.1 Adverse Events

### 7.6.1.1 Imputed AE Start Dates

Imputed AE start dates will be used to classify AEs in analysis periods, and to determine LFT elevations concurrent with AEs of interest.

Complete dates are those with non-missing day, month, and year that are valid and consistent with the standard international calendar.

- Examples of complete dates: 01JAN2013, 31DEC2013;
- Example of non-complete dates: missing, 31FEB2013, MAY2013, 2013, "unknown", "ongoing", "continuing", "NA".

Partially complete dates are those with either (1) missing day with complete month and year, or (2) missing day and month with complete year. Examples: MAY2013, 2013.

To derive the imputed AE start date and numeric imputed start date flag, the following algorithm is used if the investigator term is non-missing:

- 1. If the reported start date is complete, then the imputed start date is set to the reported start date and the numeric imputed start date flag is set to 0 (No).
- 2. If the reported start date is partially complete then the following algorithm is used:
  - a. Calculate a surrogate date as the first complete date from the following list (in order of precedence):
    - i. First active study medication date of any study medication;
    - ii. Informed consent date;
    - iii. Visit date corresponding to the visit at which the event was reported.

If a complete date is not available for any of these 3 dates, then the surrogate date is set to missing.

- b. Calculate the derived date as the earliest possible date:
  - i. If only year is provided, then set the derived date to January  $1^{st}$  of that year. e.g.,  $2004 \Rightarrow 01$ JAN2004

- ii. If year and month are provided, then set the derived date to the first day of the month. e.g., AUG2004 => 01AUG2004
- 3. Compare the derived date with the surrogate date as follows:
  - a. If (1) the derived date is on or after the surrogate date or (2) the surrogate date is missing, then set the imputed start date to the derived date.
    - e.g., surrogate date = 05JAN2004, partial date = SEP2004, derived date = 01SEP2004 => imputed start date = 01SEP2004
  - b. If the derived date is before the surrogate date and the surrogate date is consistent with the partial date provided for the start date, then set the imputed start date to the surrogate date.
    - e.g., surrogate date = 05JAN2004, partial date = JAN2004, derived date = 01JAN2004 => imputed start date = 05JAN2004

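### A completely missing last-migraine date is set to the consent date, so an unknown interval is tabulated as 0 days and the mean of that baseline row is pulled toward recent attacks

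*SAP*

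**What the plan says.** SAP section 6.2.4.3 (Migraine History) defines the variable as "Time since last migraine (days) calculated as: (informed consent date imputed last migraine date"). The minus sign between the two dates was lost when the PDF was read; the meaning is consent date minus imputed last migraine date. The row is restricted to values "for subjects with imputed last migraine date up to 1 year before informed consent date".

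Two imputation rules feed it:

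- **Partial dates** follow the adverse-event start-date algorithm of SAP section 7.6.1.1, "but using the informed consent date as the surrogate date".
- **Completely missing dates** have their own sentence: "If the last migraine date is missing, then it will be imputed with the informed consent date". The SAP revision history lists this sentence as an addition, so it is deliberate, current text.

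SAP section 6.2.4 applies migraine history to mITT subjects, treated subjects, subjects enrolled but not randomized, and subjects randomized but outside the mITT population. It provides a not-reported "category for missing categorical variables, if applicable", and time since last migraine is continuous. Section 6.2.4.3 asks for no count or flag of imputed values and no observed-only version.

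**The concern.** Substituting the consent date does not stand in for a typical unknown value. It assigns one fixed value, zero, to everyone whose value is unknown. A last migraine taken as history cannot fall after consent in valid data, so zero is the floor and the errors cannot cancel.

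Two things are at stake in the tables that describe who was studied. The mean is too low whenever any date is missing and the true interval is not zero. And because imputed subjects are counted in n, a reader of the row cannot tell how many values were never known. If missingness differs between the four populations in which migraine history is summarised, the rule would also create apparent differences between them.

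**Working it through.** The documents give no figure for this variable, so there is none to reproduce. The check applies the SAP's formula and then sizes the result under stated assumptions.

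**Step 1: completely missing date.** Consent date minus imputed date = consent date minus consent date = 0 days. The one-year restriction does not remove a value of 0. If it were read to exclude a date equal to consent, the added sentence would have no effect on this variable.

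**Step 2: partial dates.** The algorithm in SAP 7.6.1.1 first takes the earliest possible date. If that is before the surrogate and "the surrogate date is consistent with the partial date provided for the start date, then set the imputed start date to the surrogate date". With the consent date as surrogate and consent on, say, 10 May:

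| Recorded last migraine | Imputed date | Interval |
|---|---|---|
| Completely missing | 10 May | 0 days |
| May, day unknown | 10 May | 0 days |
| Consent year only | 10 May | 0 days |
| April, day unknown | 30 April | 10 days |

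Each partial date is given the latest day that the recorded information and the consent date allow, so the interval is always the shortest possible.

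**Step 3: effect on the mean.** Let m be the share completely missing and M the mean for the rest. The reported mean is m × 0 + (1 - m) × M = (1 - m) × M. This is a proportional bias of -m if missing subjects have the same true mean as observed ones. For m = 1%, 5%, 10% and 20% the mean is 1%, 5%, 10% and 20% too low.

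**Step 4: in days, as illustration only.** Protocol section 5.2 allows 2 to 8 moderate or severe attacks per month. Two simple models for r attacks per 30 days bracket the scale:

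- Constant attack rate: M = 30/r.
- Exactly r attacks placed evenly at random in the prior 30 days: M = 30/(r + 1).

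| r | M = 30/r | at m = 10% | M = 30/(r + 1) | at m = 10% |
|---|---|---|---|---|
| 2 | 15.0 | 13.5 | 10.0 | 9.0 |
| 4 | 7.5 | 6.75 | 6.0 | 5.4 |
| 8 | 3.75 | 3.4 | 3.3 | 3.0 |

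The shift at 10% missing is thus between about 0.3 and 1.5 days. The constant-rate model fits poorly at r = 2: it leaves exp(-2) = 13.5% of subjects with no attack in the last 30 days, although inclusion criterion 2e requires at least two in each of the three months before screening.

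**Step 5: median and share at zero.** A simulation with constant attack rates (a 30.4-day month, intervals rounded down to whole days) gave:

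| r | Median, none missing | Median at 5% / 10% / 20% | Share at 0 days, none missing | Share at 0 days, 10% missing |
|---|---|---|---|---|
| 2 | 10 | 9 / 8 / 7 | 6.4% | 15.8% |
| 4 | 5 | 4 / 4 / 3 | 12.3% | 21.1% |
| 8 | 2 | 2 / 2 / 1 | 23.2% | 30.9% |

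At 1% missing the median did not move for any of the three rates.

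**Step 6: why partial dates count for less.** A date known to lie in the consent month already has a short true interval. Under the constant-rate model with whole days and the consent day uniform over a 30-day month, such subjects average about 6.7 days against 14.5 overall at r = 2, and 4.8 against 7.0 at r = 4. Setting them to 0 removes less from the mean than the same number of completely missing dates does.

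**The case against.** The strongest reply is that nothing inferential depends on this row. Time since last migraine is not the randomization stratum, a listed subgroup, a listed multiple-imputation covariate or part of any estimand. It describes the period before consent and is imputed by the same rule in every arm, so the rule favours no arm. The share of missing dates is unknown and could be zero. All of this stands, and it sets the grade.

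A reader might also infer that the rule contradicts SAP section 6.1.1: "Otherwise, all analyses will be based on observed data without using imputation". The documents do not support that. Section 6.1.1 is a general statement, and the same SAP prescribes specific date imputations for adverse events and for non-study medications. The natural reading is that a specific rule qualifies the general one.

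It might be said that the rule creates a spurious group in attack on the day of consent. That goes too far: step 5 shows a real share at 0 days without any imputation, and imputed zeros only enlarge it. Nor is missingness wholly hidden. SAP 6.2.4 provides a by-subject migraine-history listing, and table layouts sit in a separate mock document that is not available here, so a footnote or count there cannot be excluded.

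None of this rescues the rule itself. It still enters a value of zero for subjects whose value is unknown.

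**Conclusion.** The rule is wrong as written, and the matter is minor. By the SAP's own formula, each completely missing date becomes 0 days, the minimum, and the subject still counts in n. The mean of this row is biased toward recent attacks by the factor (1 - m), assuming that missing subjects resemble observed ones. The documents do not give m, and there is no effect if m is 0. The figures in days depend on an assumed attack pattern and show scale only.

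Three stronger readings should be avoided. The median is not necessarily lowered; it may stay where it is at small missing shares or high attack frequency. Partial dates push the same way, but they cannot simply be added to m, because their true intervals are already bounded. And no efficacy result or safety test is affected.

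**What to change.** In SAP section 6.2.4.3, replace the sentence on missing dates with: *If the last migraine date is completely missing, time since last migraine is left missing.* Show n and the number not reported for this row in each migraine-history table.

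Replacing the sentence is safer than deleting it. Step 4 of the algorithm in section 7.6.1.1 also assigns a default date when nothing usable is recorded, and a programmer could fall back on it and reach the consent date again.

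The replacement does not touch partial dates. Optionally, add a second sentence that leaves the interval missing for partial dates, or uses the midpoint of the possible range ending at consent.

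The cost is a slightly smaller n in one descriptive row. No new data are needed and no test changes.
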